#### **4 STUDY DESIGN**

This is an observational, cross-sectional study of children (aged 8 to 18) presenting with shoulder instability of any origin, traumatic or atraumatic (n=15) and an age-matched sample (n=15) with no history of shoulder problems. Muscle activity and movement pattern differences will be measured using non-invasive 3D motion capture and surface electromyography, to identify factors responsible for instability. Only a single visit to the site will be required (ORLAU, RJAH). No interventions or treatments are included in this study as this is an observational, cross-sectional study.

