## STUDY FLOWCHART

## 1 BACKGROUND

The aim of this study is to identify factors responsible for recurrent shoulder instability in children. Shoulder instability, i.e. complete or partial dislocation of the shoulder joint, is common in children, resulting in pain and disability. Recurrent instability can damage the shoulder joint resulting in the premature development of arthritis.

Rehabilitation approaches are preferred over surgical methods for the growing child e.g. physiotherapy to restore movement and prevent further instability. Existing rehabilitation procedures are based on addressing factors assumed to be responsible for instability e.g. physiotherapists may try to increase shoulder stability by building up the shoulder muscles to compensate for the damaged ligaments. It is evident however that we do not fully understand the mechanisms of shoulder instability as failure rates for physiotherapy are high, with 70% - 90% of children continuing to suffer recurrent instability. This is an observational, cross-sectional study of children (aged 8 to 18) presenting with shoulder instability of any origin, traumatic or atraumatic (n=15) and an age-matched sample (n=15) with no history of shoulder problems. Muscle activity and movement pattern differences will be measured using non-invasive 3D motion capture and surface electromyography, to identify factors responsible for instability. Only a single visit to the site will be required (The Orthotic Research & Locomotor Assessment Unit (ORLAU) based at The Robert Jones & Agnes Hunt Orthopaedic Hospital NHS Foundation Trust in Oswestry.).

If we better understand the mechanisms associated with instability, we can better target physiotherapy interventions to reduce dislocations and disability. If we identify specific patterns of activity associated with instability, these could be addressed through personalised and improved exercise prescription and rehabilitation. Additionally, we may identify causes of instability for which physiotherapy may not be appropriate, therefore ensuring patients are referred to the correct service in a timely manner, improving patient outcomes and allocating physiotherapy resources more appropriately. Participants will be recruited from musculoskeletal/orthopaedic outpatient clinics. This study is funded by the Private Physiotherapy Education Foundation.

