## 2 RATIONALE

Mechanisms of shoulder instability, and the subsequent development of arthritis, are poorly understood (Deitch, Mehlman et al. 2003, McFarland, Kim et al. 2003, Barden, Balyk et al. 2005, Barrett 2015). Both surgical and nonsurgical interventions are based on a current understanding of the associated mechanisms that may include anatomical predisposition (shallow glenoid, lax ligament and capsule), weak muscles, or inappropriate muscle coordination (Harryman, Sidles et al. 1992, Cordasco 2000, Inui, Sugamoto et al. 2002, Deitch, Mehlman et al. 2003, McFarland, Kim et al. 2003, Barden, Balyk et al. 2005, Hovelius and Saeboe 2009, Jaggi and Lambert 2010, Jaggi, Noorani et al. 2012, Barrett 2015, Longo, van der Linde et al. 2016, Bateman, Jaiswal et al. 2018, Best and Tanaka 2018).

Rehabilitation approaches are preferred over surgical methods for the growing child, and management is therefore aimed at addressing predominant factors associated with these mechanisms e.g. exercises to improve co-ordination of the shoulder muscles if the source of instability is dysfunctional muscle control. However, failure rates are high (approximately 70% - 90%), indicating that current understanding of these mechanisms is limited.

In children, this can have detrimental long-term effects. This research is important as shoulder instability, mainly subluxation and dislocation, is common (23.9/100,000 person years but can be as high as 164.4 for 14 -16 year olds) (Leroux, Ogilvie-Harris et al. 2015) resulting in pain, decreased movement and functional limitations. Diagnosis of shoulder instability is normally delayed (on average by 2-years) and 70% of children have repeated dislocations (Longo, van der Linde et al. 2016), often associated with premature glenohumeral arthropathy (odds ratio 19.3) (Marx, McCarty et al. 2002, Deitch, Mehlman et al. 2003).

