### 3 OBJECTIVES AND OUTCOME MEASURES/ENDPOINTS

#### 3.1 Primary objective

- The primary objective of this study is to identify factors responsible for recurrent shoulder instability in children.

In order to meet the main objective of this study, a series of secondary objectives need to be met.

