## **6 ELIGIBILITY CRITERIA**

### **6.1 Children with shoulder instability**

#### **6.1.1 Inclusion criteria**

- Children aged between 8 to 18 years of age
- Subjective reports of instability with additionally symptomatic instability in the clinical assessment criteria below
- Symptomatic instability on clinical assessment in at least one direction, confirmed by a positive clinical finding (apprehension, guarding, laxity) during the sulcus, apprehension or anterior and posterior shift load tests.
- All forms of instability including multidirectional instability, atraumatic and traumatic subluxations and dislocations.
- Children presenting with an initial or recurrent episode of instability
- Children undergoing current management or rehabilitation for their shoulder at the time of the study
- Patients with surgically managed shoulder instability who have since had a further episode of shoulder instability.

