### 7.4 Instability history

For participants identified as being eligible ONLY, the follow up questions below should be asked

	FOLLOW UP QUESTIONS		RESPONSE	
F1.	Time since last episode of instability			
	Side of instability		LEFT	RIGHT
	Dominant hand		LEFT	RIGHT
F2.	Most recent episode of instability	Partial (subluxation)		
		Full (dislocation)		
F2.	Reported direction of instability	Anterior	YES	NO
		Posterior	YES	NO
		Multi-directional	YES	NO
F2.	Previous instability episode types	Partial (subluxation)		
		Full (dislocation)		
F2.	Number of instability episodes	Partial (subluxation)		
		Full (dislocation)		

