### **Measurement burden**

In order to minimise the measurement burden on all participants and ensure the aims of the study are met, our study design has been developed following input from a Public Involvement and Engagement

(PPIE) group, an additional 7 children of appropriate age groups outside of the PPIE and clinicians who routinely work with children with shoulder instability.

A primary aim of our study is to test the reliability and variability of a measurement analysis protocol in children with shoulder instability and age-matched controls. To minimize the measurement burden on children and their parent/carer/guardian, only a single study site visit, lasting a maximum of 2 hours 30 minutes, is required. Reliability will be determined by a sensitivity analysis in which we will virtually perturbate the markers post data collection. This has been selected to minimise the measurement burden of multiple visits for children with shoulder instability and the age matched controls. For children with shoulder instability this will also minimise the variability which may arise as a result of the natural recovery process over time and confound our results. The measurement protocol has been designed after consultation with different children of appropriate age groups, clinicians and the scientific literature.

Where possible, we will additionally try and accommodate measurement sessions outside of school hours for both groups to limit any school/lesson absences.

Diaries and monthly telephone calls (lasting up to 12 months), have been selected to ensure accurate recordings of the events and minimise recall bias. We have received input re the follow up study processes and diaries from the Public Involvement and Engagement group and additional children of appropriate age groups. We do not anticipate that participants will have a large number of instability episodes and so the measurement burden for recording will be minimal. Additionally, participants will only be asked to record when an episode happens.

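### The single-session comparison of children with and without instability supports association only, yet the plan reads it as identifying responsible factors, and section 8.3 leaves the 12-month follow-up unanalysed

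*Combined protocol and SAP*

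**What the plan says.** Section 3.1: "The primary objective of this study is to identify factors responsible for recurrent shoulder instability in children". Section 8.3 opens with the same aim. Section 4 ties that aim to the measurements: "Muscle activity and movement pattern differences will be measured using non-invasive 3D motion capture and surface electromyography, to identify factors responsible for instability". Section 1 adds, as a possibility, that "we may identify causes of instability for which physiotherapy may not be appropriate".

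On design, section 4 says "Only a single visit to the site will be required (ORLAU, RJAH". Section 6.1.1 admits children after a first or a later episode and requires a positive finding on clinical testing. It also lists "Children undergoing current management or rehabilitation for their shoulder at the time of the study" and children who have had a further episode after surgery. Sections 7.1.2, 10.1 and 11 require at least 12 weeks since the last episode and set no maximum. Section 6.2.2 excludes controls with previous surgery, or with current or awaited treatment or rehabilitation, on the assessed arm.

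Section 2 describes instability as "resulting in pain, decreased movement and functional limitations". Section 7.4 records "Time since last episode of instability" and the number of episodes. The screening form in 7.1.2 records current rehabilitation and instability after surgery. Section 7.8 follows both groups monthly for up to 12 months for further episodes.

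**The concern.** Every case has already had at least one episode before the only measurement is taken. A difference from controls may have been there beforehand and contributed to instability. It may equally have followed from the injury, or from treatment that cases can receive and controls cannot. The single-session contrast looks the same under each explanation, so it does not support calling a feature responsible.

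Two conclusions are at stake. One is the headline reading of the case-control differences. The other is objective 3, which looks for features that categorise clinical presentations. With 15 mixed cases, a grouping could partly reflect how long ago the last episode was, or what treatment the child has had. Section 8.3 plans nothing that would show this.

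**Working it through.** The plan states no power, alpha, effect size or SD; section 8.1 says a power calculation is not possible and justifies 15 per group by precedent. There is therefore no figure to reproduce. The check sets the sections side by side, then counts what the follow-up could offer.

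**1. Is treatment exposure balanced between groups?** No. Section 6.1.1 lists current rehabilitation and previous surgery followed by a further episode. Section 6.2.2 excludes both for the assessed arm in controls. Whether 6.1.1 is read as permitting or requiring rehabilitation, treatment is tied to group membership.

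**2. Is there a stated route from instability to the outcome?** For movement, yes. Section 2 lists decreased movement as a result of instability, and section 8.3 reports range of movement. For muscle activity the documents are open: section 2 lists poor muscle coordination among the possible mechanisms.

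**3. Does the single visit deal with recovery?** Section 11, under measurement burden, says one visit will "minimise the variability which may arise as a result of the natural recovery process over time and confound our results". That argument explains why reliability is not tested over repeat visits. It addresses change within a child, not differences in recovery between children at their single sessions.

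**4. Does section 8.3 use the recorded history?** It plans descriptive summaries, a clustering method to be chosen later, and a conditional t-test or ANOVA. Time since last episode, episode count, current rehabilitation and post-surgical status do not appear.

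**5. Does section 8.3 use the follow-up?** No. Objective 3 mentions factors for recurrent instability, but no listed analysis relates session features to later episodes.

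**6. What could a within-case comparison offer?** Inputs: 15 cases (section 4) and 70%-90% recurrence (section 1). Section 1 gives no time frame, so applying this range to 12 months is an assumption.

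- Expected recurrence-free cases = 15 × (1 − r). For r = 0.70: 15 × 0.30 = 4.5. For r = 0.90: 15 × 0.10 = 1.5.
- Chance of two or fewer recurrence-free cases, from a binomial with n = 15 and probability 1 − r: 13% at r = 0.70, 40% at 0.80 and 82% at 0.90.
- Difference detectable with 80% power, assuming two-sided alpha 0.05 and SD = 1. The normal approximation is (1.960 + 0.842) × √(1/a + 1/b), where a and b are the numbers with and without recurrence.

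| Recurrent v recurrence-free | Normal approximation | Noncentral t |
|---|---|---|
| 10 v 5 | 1.53 SD | 1.67 SD |
| 12 v 3 | 1.81 SD | 1.96 SD |
| 13 v 2 | 2.13 SD | 2.31 SD |

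Only very large differences would be detectable, so the comparison can be descriptive and exploratory at most.

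**The case against.** The strongest reply is that this is a small observational study with mainly descriptive comparisons. It changes no treatment, and section 2 presents it as a step towards biomechanical models. The tests are conditional on a homogeneous presentation and the clustering method is deferred, so heterogeneity is partly foreseen. Section 1 also speaks once of patterns associated with instability. All of this stands and limits the harm. It does not change the aim stated in 3.1, 4 and 8.3, which goes further than the design allows.

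Four stronger readings are tempting, and the documents do not support them.

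- A reader might infer that cases are measured at any stage of recovery. They are seen no earlier than 12 weeks after an episode, must still test positive, and are excluded if surgery was followed by no further episode. This narrows the spread, although time since the episode has no upper bound.
- A reader might infer that the plan concedes altered muscle activation to be a consequence of instability. Section 2 says this of pain, movement and function only.
- A reader might infer that the study is purely cross-sectional. The follow-up in 7.8 makes session features precede later episodes; what is missing is the analysis.
- A reader might infer that the study would direct physiotherapy at after-effects. Section 1 offers clinical use only as a conditional hope.

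It is also fair to say that displays by recovery and treatment status cannot separate cause from consequence. They show how far a pattern tracks those items; the change of wording is what corrects the claim.

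**Conclusion.** The concern holds as a mismatch between claim and design. The single-session contrast can show patterns associated with having shoulder instability. It cannot show that they are responsible for it, because episodes, and in some children treatment, precede the measurement and treatment differs between groups by design.

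No numerical size can be given for the distortion. The documents supply neither the share of cases in rehabilitation nor the effect of recovery on any feature, and rehabilitation could move cases towards controls as well as away. A larger sample would not resolve it.

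For recurrence, the follow-up offers temporal order within cases, but section 8.3 leaves it unused. The expected 1.5 to 4.5 recurrence-free cases of 15 rests on applying the 70%-90% in section 1 to 12 months. Even then, precedence would not prove cause, since session features may still reflect earlier episodes or treatment. The point should be settled in the wording and in 8.3 before analysis.

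**What to change.** 1. In sections 3.1, 4 and 8.3, describe the single-session case-control differences as *patterns associated with shoulder instability*. The matching sentence in section 1 should follow.
2. In section 8.3, add a descriptive, exploratory comparison, within cases, of session features against recurrence over 12 months. Reserve *factors for recurrence* for that comparison. State that few recurrence-free cases are likely, with the 1.5 to 4.5 of 15 and its assumption.
3. In section 8.3, display case features, and describe any clusters, by time since last episode, current rehabilitation and previous surgery. Report number of prior episodes as part of the clinical presentation, not as a nuisance factor. Do not label a cluster a clinical presentation without showing this breakdown.

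No new visits, measurements or participants are needed: the items are already collected under 7.1.2, 7.4 and 7.8. The cost is amended wording, a few extra tables and plots, and a weaker headline claim.

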#### **5 STUDY SETTING**

The research site is located at the RJAH Orthopaedic Hospital NHS Foundation Trust in [name].

The movement analysis sessions will take place at the Orthotic Research & Locomotor Assessment Unit (ORLAU) based at RJAH Orthopaedic Hospital NHS Foundation Trust in Oswestry.

Our main recruitment site is based at RJAH, [name]. Potential participants on their routine hospital or health service visits, who fit the inclusion/exclusion criteria, will be given brief information about the study by their treating physician/surgeon/therapist. If potential participants express an interest in the study the treating physician/surgeon/therapist may also pass on the relevant contact details to the study team. Risk mitigation against under recruitment will be achieved by recruiting from a further patient identification centre sites Shrewsbury and Telford NHS TRUST, UHNM, Stoke and other relevant health care services such as GP practices and additional outpatient services in the second. We will also disseminate information about the study using social media.

## **6 ELIGIBILITY CRITERIA**

### **6.1 Children with shoulder instability**

#### **6.1.1 Inclusion criteria**

- Children aged between 8 to 18 years of age
- Subjective reports of instability with additionally symptomatic instability in the clinical assessment criteria below
- Symptomatic instability on clinical assessment in at least one direction, confirmed by a positive clinical finding (apprehension, guarding, laxity) during the sulcus, apprehension or anterior and posterior shift load tests.
- All forms of instability including multidirectional instability, atraumatic and traumatic subluxations and dislocations.
- Children presenting with an initial or recurrent episode of instability
- Children undergoing current management or rehabilitation for their shoulder at the time of the study
- Patients with surgically managed shoulder instability who have since had a further episode of shoulder instability.

#### **6.1.2 Exclusion criteria**

- Children with co-existing neurological pathologies or deficits
- Surgically managed patients who have not had episodes of instability following the intervention.

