Shoulder stability results from complex mechanisms comprising finely balanced forces in ligaments, muscles and joint surfaces. These can be disrupted in a range of neuromuscular disorders and joint degradation, and are vulnerable to traumatic injury. Currently, we are unable to capture this complexity to quantify instability during dynamic upper limb tasks performed during clinical assessment and rehabilitation (Marchi, Blana et al. 2014). Biomechanical or mathematical modelling of this complex structure can help to understand the mechanisms associated with instability and predict outcomes for surgical and non-surgical interventions. Loading on internal structures that cannot be measured can also be estimated by this approach. Furthermore, approximately 30% of patients who have surgical stabilisation of their shoulder go on to sustain further episodes of instability (Deitch, Mehlman et al. 2003).

This project is therefore a fundamental step, in the development of biomechanical models which can ultimately be used to further our understanding of the shoulder, specifically behaviour of the articulating bony surfaces and muscle forces.

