#### **6.2.2 Exclusion criteria**

- Any previous presentation to a health care professional with a diagnosis of shoulder instability
- Children with a previous shoulder injury within the last 3 months on the arm being assessed that has not resolved
- Children with co-existing neurological pathologies or deficits
- Children who have had a previous surgical intervention on the arm being assessed
- Children currently undergoing or awaiting medical management, diagnostic investigations or rehabilitation on the arm being assessed

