### 7.1.2 Screening for children with shoulder instability

Area's in highlighted in grey must have a positive response to be eligible for the study.

	CRITERIA	YES	NO	CHECK
1.	A minimum of 12 weeks since last shoulder instability episode			
2.	Aged between 8 to 18 years			
3.	3a. Initial episode of shoulder instability OR			
	3b. Recurrent episode of shoulder instability			
4.	Subjective report of instability			*
5.	Symptomatic instability in at least one direction , confirmed by a positive clinical finding of  - Apprehension - Guarding - Laxity	5a. Sulcus (inferior)		
		5b. Anterior shift load		
		5c. Posterior shift load		
		5d. Apprehension relocation		
6.	Currently undergoing rehabilitation			
7.	Shoulder instability episode following surgical management of shoulder instability			
8.	No co-existing neurological pathologies or additional musculoskeletal injuries to the upper limb being assessed			

\*if yes must have a positive response to question 5.

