### 7.1.3 Screening for age matched controls

All screening questions must have a positive response to be eligible for the study

	CRITERIA	YES	NO	CHECK
1.	Aged between 8 to 18 years			
2.	NO previous presentation to a health care professional with a diagnosis of shoulder instability			
4.	NO history of shoulder injury within the last 3 months on the arm being assessed			
5.	NO co-existing neurological pathologies or deficits			
6.	NO previous surgical intervention on the arm being assessed			
7.	NOT currently undergoing or awaiting medical management, diagnostic investigations or rehabilitation on the arm being assessed			

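### Surgery for instability on the measured arm can occur only in cases already recurrent at entry, and section 8.3 plans nothing to separate its effect

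*Combined protocol and SAP*

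**What the plan says.** Section 6.1.1 admits to the case group "Patients with surgically managed shoulder instability who have since had a further episode of shoulder instability". Section 6.1.2 excludes "Surgically managed patients who have not had episodes of instability following the intervention". Unoperated children may enter with either an initial or a recurrent episode.

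For controls, section 6.2.2 excludes "Children who have had a previous surgical intervention on the arm being assessed", and section 7.1.3 repeats this as a screening item that every control must meet. Section 6.2.2 also excludes "Any previous presentation to a health care professional with a diagnosis of shoulder instability", with no arm specified.

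Question 7 of the case screening form (section 7.1.2) records "Shoulder instability episode following surgical management of shoulder instability" as yes or no. It does not ask which arm was operated on. The instability history form in section 7.4 has no field for surgery.

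The aim is stated in section 3.1: "The primary objective of this study is to identify factors responsible for recurrent shoulder instability in children". Section 8.3 plans group means and SDs, muscle activity summaries, and a clustering or categorisation method to be chosen once the data are known. If the sample allows, a t-test or ANOVA follows between the groups so found. Prior surgery is not mentioned there as a stratum, an adjustment or a sensitivity analysis.

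**The concern.** An operation on the shoulder may leave lasting changes in range, activation or the sEMG signal. In this dataset any such change would sit in the case group alone, and within it only among children who had already had a further episode. It would contribute to the case-control difference and also to any contrast between recurrent and first-episode cases. With 15 cases, a few operated shoulders could also form a cluster of their own.

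Because surgery carries no label in the planned analysis, such a feature or cluster could be taken for a pattern of instability or a factor for recurrence. The primary objective and objective 3 would then be answered in part by the after-effects of an operation.

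**Working it through.** There is no power or precision figure in the plan to reproduce. Section 8.1 says a power calculation is not possible and bases 15 per group on earlier measurement protocols.

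**Step 1: where operated arms can appear** (sections 6.1.1, 6.1.2, 6.2.2, 7.1.2 and 7.1.3)

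| Assessed arm | Case, first episode | Case, recurrent at entry | Control |
|---|---|---|---|
| Never operated | possible | possible | possible |
| Operated on for instability | not possible | possible | not possible |
| Operated on for another reason | not ruled out | not ruled out | not possible |

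The second row is the point: recurrence at entry varies among unoperated cases but is fixed among those operated on for instability. The third row shows the limit of question 7, which does not cover surgery for other reasons.

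**Step 2: shift in the case mean.** Let k be the number of operated cases and d the lasting effect of surgery in SD units. Neither is in the documents, so both are assumed. With no true instability effect, the spurious case-control difference is (k/15) × d.

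| k | d = 1 | d = 2 |
|---|---|---|
| 0 | 0 | 0 |
| 2 | 2/15 × 1 = 0.13 SD | 2/15 × 2 = 0.27 SD |
| 3 | 3/15 × 1 = 0.20 SD | 3/15 × 2 = 0.40 SD |
| 5 | 5/15 × 1 = 0.33 SD | 5/15 × 2 = 0.67 SD |

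For scale, the standard error of a 15 v 15 difference is sqrt(2/15) = 0.37 SD. The shift at d=1 is about a third of that for k=2 and just over half for k=3.

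**Step 3: effect on a test, for illustration only.** A two-sided 5% t-test of 15 v 15, simulated with 20,000 runs per setting and d from 1 to 2, rejects in 5.6% to 6.8% of runs for k=2, 7.3% to 11.2% for k=3, and 11.6% to 26.9% for k=5. With k=0 it is 5%. Section 8.3 does not commit to this test between cases and controls, so these rates only indicate scale.

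**Step 4: within the cases.** Assume 70% of unoperated cases are recurrent at entry. For k=3 there are 12 unoperated cases, about 8 recurrent and 4 first-episode. Operated children are then 3/(3+8) = 27% of recurrent cases and 0 of 4 first-episode cases. At d=1 the recurrent mean shifts by 0.27 SD relative to the first-episode mean. For k=2 the share is 2/(2+9) = 18%, a shift of 0.18 SD.

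**Step 5: cost of leaving them out.** The standard error without operated cases is sqrt(1/(15−k) + 1/15): sqrt(1/13 + 1/15) = 0.38 SD for k=2 and sqrt(1/12 + 1/15) = 0.39 SD for k=3, against 0.37 SD with all cases.

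**The case against.** The entry rules are what the case definition requires. Cases must have symptomatic instability, so an operated and stable child is not a case. Controls are meant to have no history of shoulder problems, so barring operated arms is ordinary. This stands, and a reader who inferred that eligibility should change would go further than the documents support.

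A reader might also contrast the rationale's statement that "approximately 30% of patients who have surgical stabilisation of their shoulder go on to sustain further episodes of instability" with the fact that every enrolled child operated on for instability has had a further episode. That contrast measures no bias: a child operated on for instability who has another episode is recurrent by definition.

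Nor is recurrence in this study settled wholly by entry. Sections 3.2 and 7.8 count new episodes by diary and monthly calls for up to 12 months, and on that count an operated case may or may not recur. However, section 8.3 gives no analysis linking these counts to movement features or to surgery, so the follow-up does not resolve the point as planned.

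The number of operated cases may be small, since sections 1 and 2 say rehabilitation is preferred to surgery in the growing child. With k of 0 to 2 the shift at d=1 is at most 0.13 SD. This stands, and it keeps the point modest. The comparisons are also largely descriptive, and an operated cluster might be noticed on inspection, but nothing in the plan requires anyone to look.

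Finally, the plan deliberately enrols children with further episodes after surgery and targets all forms of instability. Making unoperated cases the main set would narrow that target and shrink a small sample. For that reason the remedy belongs in a secondary analysis.

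**Conclusion.** The point holds as a gap in the analysis, not as a fault in eligibility. Surgery for instability on the measured arm coincides by rule with case status and with recurrence at entry, and section 8.3 has nothing that would separate them. A lasting effect of surgery could therefore be reported as a feature of instability or recurrence.

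The size depends wholly on two figures the documents do not give. For two or three operated cases and an assumed effect of 1 SD, the case mean moves by 0.13 to 0.20 SD, which is below the standard error of the comparison. If no operated child enrols, there is no effect. A reader might take a larger figure, such as 5/15 × 1.5 = 0.50 SD, as the likely bias, but that needs a third of the cases to be operated, and nothing in the documents supports it.

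This is an inexpensive improvement worth making before the data are seen, particularly as the clustering method is still open.

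**What to change.** In section 8.3:

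- Keep all cases as the main set.
- Identify operated cases by screening question 7, and confirm that the surgery was on the assessed arm. The form does not record side, so this needs one added entry, taken from the family or from the NHS record, which section 9.2 lets the team see after consent.
- State k and show the operated cases separately in the kinematic, kinetic and muscle activity summaries.
- Pre-specify a repeat of the case-control summaries and of the objective 3 search without the operated cases.
- Report any feature or cluster that disappears in the repeat as possibly due to surgery, not as a factor for recurrent instability.

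No change to eligibility, visits or measurements is needed. The cost is a secondary set smaller by k and a little more analysis. Two limits should be stated. Question 7 does not capture surgery for other reasons, so a reader should not assume that it finds every operated arm. A feature may also disappear because of the smaller numbers alone, which is why the wording is possibly due to surgery.
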